Methods: Participants who meet the inclusion criteria will be randomly assigned to the TEHE only or Acupressure only or combined acupressure and TEHE (TEHE plus) or combined MBI and TEHE or control (usual care) group. All exercise groups will be offered a 12-week exercise program. They will be instructed to exercise at home to achieve weekly activity/step goals. Activity/steps and symptoms will be monitored daily using the FitBit and a smart phone application. Weekly summary report of physical activity and symptoms will be sent to participants through a web-based mobile phone application. In addition to the TEHE, the TEHEplus group will receive instructions on how to locate and apply the pressure on the acupressure points and weekly recommendation for acupressure points. The acupressure only group will receive only instruction on how to apply the pressure on the acupressure points through the online training or in person training with weekly recommendation for acupressure points. The MBI+TEHE group will receive a weekly recommendation to add mindfulness based intervention including body scan mindful breathing, and mindful movement. The control (usual care) group will report their symptoms level and monitor physical activity through Fitbit and smartphone application daily. At the end of week 12, in addition to the questionnaires, participants will answer open-ended questions about their opinions on the program. Symptoms will be assessed and blood will be drawn before and after the program. Participants who enrolled in the sub-study will be scheduled for one visit for an MRS.

2. Objectives (include all primary and secondary objectives)

Purpose/Specific Aims:

The study primary aims are to (1) test the feasibility of a 12-week technology-enhanced home exercise (TEHE) program and combined technology-enhanced home exercise and Acupressure (TEHEplus) program among cancer survivors; (2) to determine the effect of the TEHE plus program on fatigue, physical activity and serum biomarkers (Heat Shock Protein 90 and Brain-Derived Neurotrophic Factor) compared to the control (usual care) group.

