Once the informed consent is signed, instruction video on how to install a smartphone application and activity tracker (Fitbit), study materials will be sent to the participant. The participants will be meet with a research team member online using the participant's preferred method (e.g., FaceTime, Zoom, etc.) to review the equipment instruction, and measure cognitive function and perceived short physical performance online. If travel is feasible, participants will be meet with the research team member in person at the East Baltimore (Wald) Community Nursing Center and Outreach or Sidney Kimmel Comprehensive Cancer Center to set up the study device and measure muscle strength, physical performance and heart rate variability (table 1). Participants will be asked complete the questionnaire package through Redcap survey. The physical activity tracker (Fitbit) and the mEMA application will be installed on the participants' smartphone with written instructions on how to use both devices. Participants will be asked to wear the Fitbit on the non-dominant arm and respond to the mEMA daily for 12 weeks.

Peripheral blood will be drawn at week 1 and week 12 for participants who can complete the study visit in person by a registered nurse or trained research staff at the East Baltimore (Wald) Community Nursing Center and Outreach or at the phlebotomy (research clinical blood draw) at Sidney Kimmel Comprehensive Cancer Center, Johns Hopkins University. The collection of blood samples by venipuncture in this study will include the amount of 15 mL, one time per study visit, 2 visits in 12 weeks. (Confirmation that the blood collection by venipuncture from study subjects, the amounts were drawn will be less than 550 ml in 8 weeks and collection occur less than 2 times per week). Blood will be transferred and processed at the Johns Hopkins School of Nursing biophysiological laboratory.

Sub-study (MRS imaging):

Participants enrolled in the sub-study will be scheduled for the MRS at the National Institute on Aging (NIA) located at Medstar Harbor Hospital. The MRS will be done by the NIA staff. The research assistant will accompany the participants and a registered nurse will be available for consultation throughout the MRS process. Only de-identified data will be shared with the Medstar for data analysis.

Table 1: Data collection process

Tasks	Study visit 1	Weeks											Study visit 2	
		Baseline	1	2	3	4	5	6	7	8	9	10	11	

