Demographic and disease information questionnaire	X													
FACT-F and PROMIS fatigue	X													X
PROMIS Adult profile	X													X
Cognitive function (MOCA and MASQ)	X													X
Physical activity (steps) and HR (from the wearable device)*	X	X	X	X	X	X	X	X	X	X	X	X	X	X
Muscle strength test	X													X
Short-form survey (SF-36)	X													X

Date: September 26, 2024

Principal Investigator: [name]

Application Number: IRB00154198

Connor-Davidson Resilience Scale	X									X
Coping self-efficacy scale	X									X
Pittsburg Fatigability Scale (PFS)	X									X
Physical performance	X									X
Heart rate variability	X									X
Blood sample for HSP90 and BDNF level	X									X
Open-ended questions about the feasibility of the program										X
MRS for the central and peripheral markers (sub-study)	X									

Randomization:

After the baseline data collection and blood draw, the participants will be stratified by type of cancer (breast cancer vs. prostate cancer), age, and treatment (completed treatment vs. receiving immunotherapy). Participants will be randomly assigned to the control and intervention (TEHE only, TEHE plus, Acupressure only, TEHE +MBI groups) groups. The participants' random group assignment will be determined using the Excel program.

Participants in the experimental groups will receive either a) 45-60 min online exercise training/consultation session only, b) an online exercise training session and online and written APA instruction (TEHE +Acupressure group), c) online and written APA instruction only or d) exercise training instructions and mindfulness relaxation instructions (TEHE + MBI groups). After the exercise training session, participants will select their preferred exercise type and their preferred follow-up methods, duration of exercise, exercise schedule, and exercise frequency for the next 12 weeks. Participants will receive weekly recommendation for physical activity goals, recommended acupressure points (for TEHEplus and Acupressure only groups) and recommended mindfulness techques (for TEHE + MBI group). Participants in the control group will continue with their daily usual physical activity.

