The mean and standard deviation of each outcome measure, recruitment rate, drop out, acceptability, tolerability will be calculated per group per study visit. The study primary aim the feasibility of a 12-week technology-enhanced home exercise (TEHE) program and TEHE plus program (***Aim 1***) will be analyzed using descriptive statistics of eligible participants and recruited participants, a number of participants completing the intervention program, compliance (number of participants complete the daily step goal), and participants' satisfaction and opinion of the intervention. To examine the effect of the TEHE program on fatigue, physical activity and serum biomarkers (Heat Shock Protein 90 and Brain-Derived Neurotrophic Factor) (***Aim 2***), the paired t-test will be used to analyze the effect of the program on fatigue, PA and biomarkers at the end of the program compared to baseline. The student t-test will be used to compare the variables among participants in the TEHE program, Acupressure only, TEHEplus, and TEHE +MBI compare to the usual care (control) group.

The secondary aims: The change of fatigue and physical activity level in week 12 compared to baseline will be calculated. Analysis of Variance (ANOVA) will be used to compare the effect of the TEHEplus, combined TEHE, and MBI with the TEHE only and Acupressure only on fatigue and physical activity (***Aim 3***). Change from baseline to 12 weeks will be computed for serum HSP90AA1 and BDNF levels. ANOVA will be used to examine the differences of change in serum biomarkers at week 12 compared to baseline in the TEHE only, Acupressure only, TEHEplus, TEHE +MBI and control (usual care) groups (***Aim 4***).

Sample size justification

Sufficient information from prior studies is not available for us to conduct a sample size calculation for the proposed multilevel analyses. The purpose of this pilot project is to explore the feasibility of the program and the relationships between the trajectories of the outcome measures, and not to achieve high power. The proposed N of 110 (22 participants/group) will likely result in low (below 0.60) statistical power. Results obtained will inform future power analyses for full-scale studies.

Early stopping criterion for safety/futility/efficacy as needed.

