5. The MBI and responding to the questionnaire has no medical risk. Participants will be asked to spend 20-30 min completing the questionnaire and listening to the instructions on how to use the smartphone application and Fitbit. All subjects will be informed that they can stop answering questions if they feel tired; they can resume the questionnaire at a later time. Participants will spend less than 5 min responding to a short survey on fatigue level, daily, through the application. Participation in this study involves the completion of questions (4 questions) about depressive symptoms. Scores from these questions (range from 4-20) would not be a sufficient basis for clinical decisions or diagnosis, contain substantial margins of error, and are not used for diagnostic purposes in this study. This score might hint at health conditions. Therefore, participants will receive the score for this depressive symptom subscale. If the depression score is higher than 16 (T score of > 70: severe depressive symptom), a registered nurse will suggest the participant discuss this issue with his/her primary health care provider.
6. Magnetic Resonance Spectroscopy (MRS)
There is a risk for injury from the magnetic resonance imaging (MRI) magnet if the participant has some type of metal in their body. It may be unsafe to have an MRI scan if the participant has a pacemaker or other implanted electrical device, brain stimulator, some types of dental implants, aneurysm clips (metal clips on the wall of a large artery),

Date: September 26, 2024

Principal Investigator: [name]

Application Number: IRB00154198

metallic prostheses (including metal pins and rods, heart valves, and cochlear implants), permanent eyeliner, implanted delivery pump, or shrapnel fragments.

Welders and metal workers may have small metal fragments in the eye. Each participant will be screened for such metal before having any scan. If the participant has any metal, they will not receive an MRI scan. If the participant has a question about metal in their body, they should inform the research team.

Each participant will be asked to complete an MRI screening form before each MRI scan. All magnetic objects must be removed before entering the MRI scan room. This includes items like watches, coins, jewelry, and credit cards.

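### Steps are recorded throughout the 12 weeks in every arm, but Aims 2 and 3 test physical activity only on baseline and end of program, so early leavers are lost and precision with them

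*Combined protocol and SAP*

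**What the plan says.** **Collection.** Section 4 (Data collection schedule and procedures) tells participants, before any arm is assigned: "Participants will be asked to wear the Fitbit on the non-dominant arm and respond to the mEMA daily for 12 weeks". The Methods paragraph of the abstract says "Activity/steps and symptoms will be monitored daily using the FitBit and a smart phone application", and for usual care "The control (usual care) group will report their symptoms level and monitor physical activity through Fitbit and smartphone application daily". Table 1 marks the row "Physical activity (steps) and HR (from the wearable device") in every column. The row "FACT-F and PROMIS fatigue" is marked at the two study visits only. Section 8 adds a daily app item: "Participants will spend less than 5 min responding to a short survey on fatigue level, daily, through the application".

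**Analysis.** Section 7 (Analysis plan) states for Aim 2 that "the paired t-test will be used to analyze the effect of the program on fatigue, PA and biomarkers at the end of the program", against baseline, followed by Student t-tests of the active arms against usual care. For Aim 3, "The change of fatigue and physical activity level in week 12 compared to baseline will be calculated" and the active arms are compared by ANOVA. Tracker data otherwise enter only the Aim 1 compliance summary. No analysis population, missing-data rule or imputation is given.

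**Leaving early.** Participants may withdraw at any time (section 4) and are then asked to return the tracker (section 10). Those whose condition worsens are removed (section 4), and some complications can end participation (section 7).

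**Unreconciled wording.** The design is called repeated measures. The sample-size paragraph describes multilevel analyses as proposed and mentions trajectories of the outcomes. No such model appears in the analysis plan.

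**The concern.** A paired t-test or an ANOVA on change needs a value at both ends. A participant who leaves in week 10 has many weeks of steps on file, measured with the same instrument as the endpoint, and none of them counts. Physical activity is a primary outcome under Aim 2, power is already stated to be below 0.60, and the results are meant to feed power calculations for a larger trial. Throwing away usable data makes the estimate noisier than it need be. If leaving is related to steps and differs between arms, the estimate may also be biased.

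**Working it through.** **1. The plan's own figure.** The only one is power below 0.60 with 22 per group. No effect size, SD or alpha is given, so it cannot be reproduced. Worked backwards at two-sided 0.05, a t-test with 22 per group has power 0.60 at a standardised difference of 0.683, so the statement fits any smaller effect. At an assumed difference of 0.50, power is 0.37 with 22 per group, 0.31 with 18 (about 20% lost) and 0.26 with 15 (about 30% lost).

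**2. Standard error when dropout is random.** From the documents: 22 per arm, baseline plus 12 weekly values. Assumed: 20% or 30% dropout spread evenly over weeks 3-12; correlation between weeks c + (1-c)r^lag with c = 0.6 or 0.7 and r = 0.5 or 0.8. That gives about 0.60-0.72 between baseline and week 12, and 0.80-0.94 between adjacent weeks. The unit is the between-person SD of weekly steps; m = 22(1-p) completers per arm; rho is the baseline to week-12 correlation.

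- Completers' change score: SE = sqrt[4(1-rho)/m]. With rho = 0.60 and p = 0.2: m = 17.6, sqrt(1.6/17.6) = 0.301.
- Completers, baseline-adjusted: SE = sqrt[2(1-rho^2)/m] = sqrt(1.28/17.6) = 0.270.
- Mixed model on all observed weeks: generalised least squares with known covariance, baseline mean either free in each arm or common to both.

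| rho (adjacent weeks) | Dropout | Change score | Baseline-adjusted completers | Mixed, free baselines | Mixed, common baseline | Change / common |
|---|---|---|---|---|---|---|
| 0.60 (0.80) | 0% | 0.270 | 0.241 | 0.270 | 0.241 | 1.118 |
| 0.60 (0.80) | 20% | 0.301 | 0.270 | 0.289 | 0.263 | 1.148 |
| 0.60 (0.80) | 30% | 0.322 | 0.288 | 0.302 | 0.277 | 1.165 |
| 0.72 (0.94) | 0% | 0.225 | 0.209 | 0.225 | 0.209 | 1.078 |
| 0.72 (0.94) | 20% | 0.252 | 0.234 | 0.240 | 0.225 | 1.120 |
| 0.72 (0.94) | 30% | 0.269 | 0.250 | 0.250 | 0.235 | 1.145 |

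Over all settings with dropout, including a random-intercept-and-slope covariance (ratios 1.100 and 1.127), the change-score SE is 10-17% larger. The zero-dropout rows show that part of this is only the use of change scores in place of baseline adjustment. The leavers' own weeks account for 4-8% (change score against free baselines), or 3-7% against baseline-adjusted completers. With the abstract's total of 105 (21 per arm), all SEs grow by sqrt(22/21) = 1.02 and the ratios do not move.

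**3. Bias when dropout depends on steps.** No true effect; same covariances; 20% or 30% leave each arm, at random in usual care and selectively in the exercise arm (odds of leaving up 2.7-fold per SD).

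| What drives leaving | Raw week-12 means | Change from baseline | Mixed model |
|---|---|---|---|
| Low level of steps in weeks 1-2 | +0.11 to +0.19 | -0.02 to -0.06 | within 0.01 |
| Poor early change from baseline | about 0 | +0.05 to +0.10 | within 0.01 |

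Variants of the second mechanism put the change-score bias as high as +0.12. A random-slope version, with 30% against 10% dropout and the steepest dependence, gave 0.15 SD of change for completers and about 0 for the model. Other ways of simulating the first mechanism give up to about +0.2 for raw means, and up to about 0.04 for the model.

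**4. Two limits.** With the same dropout rate and mechanism in both arms, both methods are nearly unbiased (0.48-0.51 for a true 0.50). If leaving depends on steps that were never observed, at 30% against 10% and a true 0.50, completers give 0.60-0.65 and the model 0.54-0.56: less bias, but not none.

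**The case against.** The strongest objection concerns bias. A reader might infer that the planned analysis overstates the program's effect, because people with low step counts leave the exercise arms. The documents do not support that. The outcome is defined as change, and when leaving follows a low level of steps the completers' change score is biased slightly downward. The upward figure of about +0.2 SD needs raw week-12 means, which is only one possible reading of the Aim 2 Student t-test. No dropout rate is given, and the low adherence cited in the Background concerns exercise regimens, not study withdrawal or a difference between arms. An argument about leaving more often than usual care also cannot touch Aim 3, whose physical-activity ANOVA compares active arms only. All of this stands.

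A reader might also infer that daily app ratings would rescue the fatigue result. They are a different measure from FACT-F and PROMIS and cannot recover a missing second-visit score. That stands too.

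The plan never says completers only; the loss follows from the named tests and the absence of any missing-data rule. This is also a low-powered pilot, and a bias of 0.12 SD is under half of a standard error of about 0.3. That limits the weight of the point. It does not justify leaving collected data unused when the sample-size text already presumes a longitudinal analysis.

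**Conclusion.** The concern holds for physical activity, chiefly as a loss of precision and as an unreconciled conflict between the multilevel wording and the two-time-point tests. The standard error of the week-12 contrast is about 10-17% larger than it need be. This rests on assumed dropout of 20-30%, assumed correlations and a known covariance; estimating the covariance will reduce the gain somewhat, and lower dropout will reduce the share due to leavers.

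Bias is possible but unsettled: about -0.06 to +0.12 SD for change in the main settings, somewhat more under steep selection, and near zero if dropout is alike across arms. The model removes it only when leaving depends on observed steps. The point should be acted on, but it does not show that the planned result would be inflated.

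**What to change.** For physical activity in Aims 2 and 3, analyse weekly mean steps, baseline included, for all randomised participants with a mixed model:

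- baseline as a covariate, or constrained equal across arms; week; arm by week;
- a parsimonious covariance such as random intercept plus AR(1), which has 3 parameters. An unstructured matrix would need 78 for 12 weeks (12 x 13 / 2), or 91 with baseline (13 x 14 / 2), from 105-110 people;
- the week-12 change contrast as the estimate: each active arm against usual care for Aim 2, and among active arms for Aim 3.

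Define which days make up the baseline and week-12 values and how much wear makes a valid week. Keep the t-tests and ANOVA as sensitivity analyses, report dropout and its timing by arm, and reconcile the multilevel and trajectory wording with the analysis plan.

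For fatigue, keep FACT-F and PROMIS as planned; a model of weekly app ratings may be added as supportive only.

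The cost is SAP wording and modest programming. No new data are needed.

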Main Research Variable(s): The independent variables are (1) the 12-week program of TEHE alone, (2) the 12-week program of acupressure only, (3) the 12-week program of combined acupressure and TEHE (TEHE Plus), (4) the 12-week program of combined MBI and TEHE and (5) control (usual care). Outcome variables are fatigue, physical activity, contributing factors of fatigue (depressive symptom, anxiety, sleep, relationship with others), and biomarkers.

Design: Repeated measures randomized controlled trial design.

Setting: Participants will be recruited through the Comprehensive Cancer Center, Johns Hopkins University.

Sample: A total of 105 participants will be recruited from 2 populations

Population 1: Individuals diagnosed with solid tumor cancer; who had completed all primary cancer treatment (surgery, chemotherapy, and radiation therapy) within at least 3

Date: September 26, 2024

Principal Investigator: [name]

Application Number: IRB00154198

months OR prostate cancer completed all primary cancer treatment and have hormone therapy for at least 6 month, aged 21 years or older, experiencing fatigue in the past 7 days on average of $\geq 3/10$, self-report ability to complete the 6 min walk test with a perceived exertion of 6 or below on a scale 1 (hardly any exertion) to 10 (feels almost impossible to keep going), can communicate in English and own a smart phone.

Population 2: individuals diagnosed with solid tumor cancer; who are receiving immunotherapy for at least 3 months before enrollment, aged 21 years or older, experiencing fatigue in the past 7 days on average of $\geq 3/10$, self-report ability to complete the 6 min walk test with a perceived exertion of 6 or below on a scale 1 (hardly any exertion) to 10 (feels almost impossible to keep going), can communicate in English and own a smart phone.

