With the advancement of cancer diagnosis and treatment, localized cancer patients have nearly a 100% 5-year survival rate.¹ Approximately 40% of these cancer survivors experienced severe fatigue up to 2 years post-treatment, which impact the quality of life of these individuals.² Furthermore, 20% of patients receiving ICIs (PD-1/PD-L1 checkpoint inhibitors) report severe fatigue at the any-grade adverse event,³ which impact the patients' quality of life and hamper the clinical benefit with ICI.^{3,4} To date, there are no US FDA approved medications to treat cancer-related fatigue (CRF). Several clinical trials have investigated medications for CRF such as psychostimulants (e.g., Methylphenidate, Modafinil) and antidepressants (e.g., nortriptyline, amitriptyline, and bupropion), however, they have shown inconsistent results on effectiveness.⁵⁻⁸⁹ The National Comprehensive Cancer Network (NCCN; 2015) recommends five non-pharmacological interventions to manage CRF, physical activity is one of the most effective interventions for CRF.¹⁰ The American cancer society recommended 150 minutes/week of moderate-intensity aerobic physical activity (exercise performed at 60-80% of maximum heart rate) for cancer survivors with no physical limitation.¹¹ **The aerobic moderate-intensity exercise program significantly improved fatigue among cancer patients.**¹²⁻¹⁶ Cancer survivors are less likely to exercise due to the limitation of access to an exercise facility and scheduling conflict.¹⁷ To overcome these barriers, a home-based exercise intervention was used. Studies suggested a significant effect of home-based exercise on fatigue severity.¹⁴ Most home-based exercise programs were challenged by the lack of motivation and low adherence rate to the exercise regimen.¹⁸⁻²¹ The use of technology e.g., exergaming (Wii-Fit) can increase motivation and exercise adherence.²²⁻²⁴ However, the use of Wii-Fit can be limited because it required exercise equipment, television, or monitor and exercise space at home. This proposed study will use the goal-setting by using step count from the physical tracker, which will be easier to implement than exergaming and require no additional equipment and space for exercise. To enhance the effectiveness of home-based exercise on fatigue, we hypothesized combining exercise with other nonpharmacological interventions such as acupressure or mindfulness-based intervention may provide a greater effect on fatigue reduction.

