The feasibility of the TEHE plus program includes the evaluation of the recruitment and retention, acceptability, compliance, and delivery of the intervention. This study aims to measure the feasibility of the TEHE groups (including all three intervention arms). In the data collection process, the eligible participants recruited patients, a number of participants completing the intervention program will be recorded. Compliance with the intervention will be assessed using data collected from the activity tracker on minutes of moderate-intensity or greater activity. At the end of the program (12 weeks), participants will be asked to complete open questions on their satisfaction and opinion on the intervention and delivery method.

Primary and secondary objectives

The study primary aims are to (1) test the feasibility of a 12-week technology-enhanced home exercise (TEHE) program and combined technology-enhanced home exercise and Acupressure (TEHE plus) program among cancer survivors; (2) the effect of the TEHE program and TEHE plus on fatigue, physical activity and serum biomarkers (Heat Shock Protein 90 and Brain-Derived Neurotrophic Factor) compare to the control (usual care) group.

The secondary aims are (3) compare the effect of the TEHE only, Acupressure only, TEHEplus, and combined TEHE and MBI on fatigue and physical activity; and (4) determine the change in serum biomarkers at week 12 compared to baseline in the TEHE only, Acupressure only, TEHEplus, MBI+TEHE, and control (usual care) groups

Analysis plan

Exercise study:

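### The ANOVA named for Aim 3 does not isolate the benefit of adding acupressure or mindfulness to exercise; the add-on contrasts should be pre-specified

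*Combined protocol and SAP*

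**What the plan says.** Section 3 (Background) gives the reason for the combination arms: "we hypothesized combining exercise with other nonpharmacological interventions such as acupressure or mindfulness-based intervention may provide a greater effect on fatigue reduction". The secondary aim is worded more broadly. Section 7, under Primary and secondary objectives, undertakes to "compare the effect of the TEHE only, Acupressure only, TEHEplus, and combined TEHE and MBI on fatigue and physical activity", and Section 2 is similar. Usual care is not part of this aim.

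The method is in Section 7, Analysis plan. The outcome is a change score: "The change of fatigue and physical activity level in week 12 compared to baseline will be calculated". The test is then given as: "Analysis of Variance (ANOVA) will be used to compare the effect of the TEHEplus, combined TEHE, and MBI with the TEHE only" and Acupressure only. I read the phrase about combined TEHE and MBI as the single TEHE+MBI arm. The sentence therefore sets the two combination arms against the two single-component arms.

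The plan names no contrast, pairwise follow-up, confidence interval or multiplicity rule for Aim 3. The other tests in the Analysis plan do not fill the gap: the paired t-tests are against baseline, and the Student t-tests are of active arms against usual care.

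**The concern.** The question that distinguishes this trial is whether a combination does better than exercise alone. A one-way ANOVA over four arms gives an F test with 3 numerator degrees of freedom for the null hypothesis that all four means are equal. Rejection says that some mean differs, but not which one or in which direction.

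This matters here because the four arms are not alike. Three contain the exercise programme and Acupressure only does not. Physical activity is one of the two Aim 3 outcomes, so a gap between Acupressure only and the other three is easy to imagine with no add-on effect at all. The F test would then reject correctly, since the means do differ, but a reader could take the result as support for the combinations.

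The sample size section says that results should feed the power calculations of larger trials. That needs an add-on difference with its interval, which an F statistic does not supply. If the follow-up comparison is left open, it can also be chosen after the data are seen.

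**Working it through.** **The plan's own figure.** The sample size section states: "The proposed N of 110 (22 participants/group) will likely result in low (below 0.60) statistical power". The total checks: 5 × 22 = 110. The power bound cannot be reproduced, because no test, outcome, effect size, SD or alpha is given. For orientation, a two-sided 0.05 comparison of two arms of 22 reaches power 0.60 at a difference of about 0.68 SD, so the bound is right for pairwise differences smaller than that.

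**Inputs.**
- Arms in Aim 3: TEHE only, Acupressure only, TEHEplus, TEHE+MBI.
- n per arm: 22 (Section 7). The Abstract says "A total of 105 participants will be recruited from 2 populations", and 105 / 5 = 21, so 21 is run as well.
- Alpha: 0.05 two-sided (assumption).
- Effect size d: 0.5, 0.65 and 0.8 SD of the change score (assumption, shown as a range).
- No dropout in the base case; the plan states no expected rate.

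**Step 1: F test when neither add-on helps.** Set TEHE only = TEHEplus = TEHE+MBI = 0 and Acupressure only = −d. The grand mean is −d/4, and the sum of squared deviations is 3(d/4)² + (3d/4)² = 0.75d². The noncentrality is λ = n × 0.75d². At n = 22 and d = 0.5, λ = 22 × 0.75 × 0.25 = 4.125; at d = 0.8, λ = 22 × 0.75 × 0.64 = 10.56. The error degrees of freedom are 4(n − 1), that is 84 or 80, and the 5% critical values of F are 2.713 and 2.719.

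| d (SD) | λ, n = 22 | P(F significant), n = 22 | λ, n = 21 | P(F significant), n = 21 |
|---|---|---|---|---|
| 0.5 | 4.13 | 0.353 | 3.94 | 0.338 |
| 0.65 | 6.97 | 0.566 | 6.65 | 0.543 |
| 0.8 | 10.56 | 0.765 | 10.08 | 0.742 |

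A simulation of the case d = 0.8, n = 22 gave 0.765.

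**Step 2: add-on contrasts in the same scenario.** TEHEplus minus TEHE only, TEHE+MBI minus TEHE only, and the mean of the two combinations minus TEHE only all have expectation 0. Each rejects 5% of the time, whatever the value for Acupressure only.

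**Step 3: precision of the add-on estimate.** With the pooled four-arm error, the 95% half-width for a pairwise contrast is t × √(2/n) SD. At n = 22 this is 1.989 × √(2/22) = 0.60 SD; at n = 21 it is 1.990 × √(2/21) = 0.61 SD. For the mean of the two combinations minus TEHE only it is 1.989 × √(1.5/22) = 0.52 SD.

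**Step 4: power when add-ons do help (n = 22, d = 0.5 / 0.8).**

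| True pattern | F test | TEHEplus − TEHE only | Mean of combinations − TEHE only |
|---|---|---|---|
| Both help, Acupressure only = TEHE only | 0.46 / 0.88 | 0.37 / 0.75 | 0.47 / 0.86 |
| Both help, Acupressure only halfway | 0.33 / 0.72 | 0.37 / 0.75 | 0.47 / 0.86 |
| Both help by d, Acupressure only worse by d | 0.91 / >0.99 | 0.37 / 0.75 | 0.47 / 0.86 |

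Neither approach has more power in general.

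**The case against.** The strongest reply has four parts.

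- **Aim 3 is worded as a general comparison of four arms, and ANOVA is a conventional match.** This stands. A reader might infer that the aim itself asks the add-on question. It does not: that question comes from the Background hypothesis, which concerns fatigue, and from the direction of the sentence in the Analysis plan.
- **Naming an ANOVA does not rule out contrasts, and the plan reports means and SDs per group and visit.** This also stands. The plan is silent rather than explicitly limited to the overall test, and a difference could be assembled from its output. The silence still leaves open which difference counts and how it is reported.
- **The F test may have more power.** A reader might infer that the ANOVA is generally less powerful than a planned contrast. Step 4 does not support that. With both add-ons helping by 0.5 SD and Acupressure only equal to TEHE only, TEHEplus minus TEHE only has power 0.37 against 0.46 for F. The argument is that F answers a different question.
- **It is a secondary aim in a pilot that disclaims high power.** This limits the consequence to interpretation, but does not remove it, because the add-on estimate and its interval are what a pilot can pass on.

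An obvious alternative, the mean of both combinations minus the mean of both single arms, is not a remedy. With no add-on benefit its expectation is d/2, because Acupressure only is half of the comparator. At 22 per arm it then rejects 21% of the time at 0.5 SD and 46% at 0.8 SD (20% and 44% at 21). It looks strong (0.64 against 0.46 for F at 0.5 SD) only when the true means match its weights.

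**Conclusion.** The point holds in this form: no stated test or interval isolates the add-on effect, and the one method named can be significant for a reason unrelated to it. The chance of that is about 35% to 76% at 22 per arm if neither add-on helps and Acupressure only is worse by 0.5 to 0.8 SD. These figures assume two-sided alpha of 0.05, equal SDs, equal allocation, no dropout and a one-way ANOVA over the four active arms. The effect sizes are illustrative, and nothing in the documents says that Acupressure only will be worse by any such amount.

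The documents do not support going further. They do not show that ANOVA wastes power in general, or that the trial cannot address the add-on question: the data and model allow it, and only the specification is missing. This should be changed, as an improvement to a secondary analysis.

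**What to change.** Replace the Aim 3 sentence with a short paragraph that fits one linear model to the change scores of the four arms and names these comparisons in advance:

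1. TEHEplus minus TEHE only (adding acupressure to exercise).
2. TEHE+MBI minus TEHE only (adding mindfulness to exercise).
3. Optional summary: mean of TEHEplus and TEHE+MBI, minus TEHE only.
4. As a separate question, TEHEplus minus Acupressure only (adding exercise to acupressure).

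Report each with a 95% confidence interval. If p-values are quoted, apply Holm and state which comparisons form the family. Keep the F test at most as a descriptive overall comparison, and say that its significance is not evidence of an add-on benefit.

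The cost is one paragraph, with no new data and no change of model. The drawback is the wide pairwise interval in Step 3, so the results should be presented as estimates for planning and not as tests of efficacy.
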